10.8 Lost to Follow-Up

Significant efforts will be made to encourage all subjects to complete the study. For subjects that are lost to follow-up the site will contact the subject's secondary contact if listed in the subject's medical record or the subject identification log as another means to contact the subject. If this is unsuccessful a final certified letter will be sent by the Investigator notifying the subject of the need and importance to follow-up.

10.9 Study Termination

The Sponsor reserves the right to terminate this study for any reason upon reasonable notice to the Investigators.

If conditions arise during the study that indicate that the study or an investigational site should be terminated, the Sponsor, Investigator, Monitor, IRB, and/or regulatory agencies will discuss the situation and take appropriate action after consultation.

Conditions warranting termination of the study or site include, but are not limited to:

- The discovery of an unexpected, serious, or unacceptable risk to subjects enrolled in the study;
- The decision on the part of the Sponsor to suspend or discontinue testing, evaluation, or development of the study device;
- Failure of the Investigator to comply with pertinent national or state regulations, IRB-imposed conditions, or protocol requirements;
- Submission of knowingly false information from the Investigator to the Sponsor, Monitor, IRB, or any regulatory agency.

11. Adverse Events

Throughout the course of the study, all AEs will be monitored and reported through the AE eCRF. If an AE occurs, the first concern will be the safety of the study subjects. All AEs occurring after study device administration will be followed until the event has resolved or stabilized or until follow-up is no longer possible.

11.1 Definitions

11.1.1 Adverse Events (AEs)

An AE is defined as any undesirable physical, psychological or behavioral effect experienced by a subject during his/her participation in a study, in conjunction with the use of the device, whether or not it is considered procedure or product related. AEs may include, but are not limited to, subjective or objective symptoms spontaneously offered by the subject, solicited via subject interviews, uncovered by review of concomitant medications or therapies, and/or observed by the Investigator. The Investigator will record the description (sign, symptom, or diagnosis), onset, resolution, seriousness, severity, cause and action taken for any event on the AE eCRF.

Disease signs and symptoms that existed prior to the study injections are not considered AEs unless the condition recurs after the subject has recovered from the pre-existing condition or the condition worsens in intensity or frequency during the study.

Commonly-reported AEs in previous studies include the following local skin changes: skin discoloration, increased sensitivity, telangiectasias in implant area, scar, edema, erythema, abscess or infection, recurrence of a pre-existing herpes labialis, ulceration, erosion or necrosis, itching or burning, pain and/or tenderness, granuloma formation, and skin blanching. Additionally, systemic findings reported in prior studies include: drop in blood pressure or anaphylactic shock, difficulty breathing, tightness in chest, shortness of breath, immune mediated diseases, tingling, numbness, temporary pain in various areas of the body, flu-like symptoms, blurred vision, or hypersensitivity to bovine collagen. The relevance of these findings to the current Bellafill product is not known.

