- 7. History of systemic granulomatous diseases active or inactive (e.g., Sarcoid, Wegeners, TB) or connective tissue diseases (e.g., lupus, dermatomyositis).
- 8. Hypertrophic acne scars, any evidence of keloid scarring in the treatment area.
- 9. Known hypersensitivity or previous allergic reaction to any of the components of the study device (including lidocaine or any amide-based anesthetic), or has a history of allergies to any bovine collagen products, including but not limited to injectable collagen, collagen implants, hemostatic sponges, and collagen-based sutures.
- 10. Undergone or be planning to undergo desensitization injections to meat products.
- 11. Unable to communicate or cooperate with the Investigator due to a language barrier (non-English speaking), poor mental development, or impaired cerebral function.
- 12. Evidence of alcohol or drug abuse (Investigator opinion), or history of poor cooperation, non-compliance with medical treatment, or unreliability.
- 13. Use of an investigational device, biologic or drug in the past 30 days, or be currently participating in an experimental drug, biologic or device trial.
- 14. Exhibits additional physical attributes which prevent the assessment or treatment of the atrophic scars, as judged by the Investigator, such as excessive hair, traumatic or surgical scars, excessive hyperpigmentation in the treatment area, etc.
- 15. Has a condition or be in a situation that, in the Investigator's opinion, may put the subject at significant risk, may confound the study results, or may interfere significantly with the subject's participation in the study.
- 16. An employee (or a relative of an employee) of the Investigator, Sponsor or representative of the Sponsor.

Study Measurements

Effectiveness:

- Acne Scar Assessment Scale (ASAS): a validated 5-point static scale assessing physician impression of acne scar severity.
- Physician Global Aesthetic Improvement Scale (PGAIS): a 5-point dynamic scale assessing cosmetic improvement.
- Subject Global Aesthetic Improvement Scale (SGAIS): a 5-point dynamic scale assessing cosmetic improvement.
- Subject QOL Impact Scale: (33 questions): a 33-question survey that allows the subject to specifically address how acne scarring has affected his/her emotional and functional status.

Safety:

• Adverse events: rate of AEs, type of AEs, relationship of AEs to Bellafill.

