1.4 Current Clinical Study

A therapy that may stimulate collagen production, such as microneedling, is potentially a useful adjunct to atrophic acne scar treatment with Bellafill. The current pilot study will evaluate the effectiveness and safety of sequential treatment of microneedling followed by intra-scar injections with Bellafill.

2. Study Objective

To evaluate the effectiveness and safety of acne scar treatment that sequentially employs microneedling followed by Bellafill injections.

3. Study Design

[figure not shown]
This is an open-label, randomized, multicenter, prospective trial assessing the efficacy and safety of microneedling treatment alone vs. microneedling treatment followed by treatment with Bellafill for correction of distensible atrophic facial acne scars.

The study is divided into two study Periods. In **Period I**, subjects will attend a Screening visit (Week -4) and undergo the Bellafill skin test. At Visit 1 (Day 0), all subjects will commence microneedling treatment for their atrophic acne scars. Subjects will then return to the clinic at Week 3 and Week 6 (Visits 2 and 3, respectively) for follow-up evaluation and additional cycles of microneedling treatment.

At Week 12 (Visit 4), all subjects commence **Period II** and are randomized to Bellafill Treatment (Track A) or to No Treatment (Track B):

- Track A: Consists of three (3) study visits. At Visit 4, subjects randomized to the "Bellafill" group will receive treatment with Bellafill for their atrophic acne scars. Subjects return for Visit 5A (Month 1 after randomization) for evaluation and follow-up, and will receive touch-up injections with Bellafill to achieve optimal correction (if necessary). Subjects will then be followed-up at Visits 6A and 7A which will occur at Month 3 and Month 6, respectively, after their last Bellafill treatment.
- **Track B:** Consists of one (1) study visit. At Visit 4, subjects randomized to the "No Treatment" group will complete visit evaluations and then return for follow-up at Visit 5B (approx. Month 3 after randomization).

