11.1.5 Relationship to Study Device

The Investigator will determine relatedness of the subject's symptom or problem to the study device or the injection procedure.

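### The pre-existing-condition rule and the relatedness question are tied to the filler injection, so microneedling events have no formal attribution category and a persisting sign in Track A could be dropped

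*Combined protocol and SAP*

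**What the plan says.** The aim in Section 2 is a sequence: "To evaluate the effectiveness and safety of acne scar treatment that sequentially employs microneedling followed by Bellafill injections". Section 3 and the visit schedule in Section 10 give microneedling to everyone at Day 0, Week 3 and Week 6. Randomization follows at Week 12, when Track A receives its first Bellafill treatment and Track B receives none.

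Section 11.1.1 opens broadly. An AE is any undesirable effect "during his/her participation in a study, in conjunction with the use of the device, whether or not it is considered procedure or product related". Onset and cause are among the items recorded for each event. A second paragraph then narrows this: "Disease signs and symptoms that existed prior to the study injections are not considered AEs". Its exception brings back a sign that returns after recovery or gets worse while the subject is on study.

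Section 11.1.5 states the whole relatedness rule: "The Investigator will determine relatedness of the subject's symptom or problem to the study device or the injection procedure". The safety measure in the synopsis is narrower still: "Adverse events: rate of AEs, type of AEs, relationship of AEs to Bellafill".

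Two neighbouring sections matter. Section 11.1.2 decides which common responses stay unrecorded, and its only yardstick is what usually follows a filler injection. Section 12.3 plans tables of AE incidence and severity and a full listing, and states no breakdown by period, track or relatedness.

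**The concern.** The two narrowing rules read as if the study began with the filler. Here the first treatment is microneedling, and the first Bellafill treatment comes 12 weeks later in only one of the two tracks. A pre-existing-condition rule should separate what the subject brought into the study from what arose in it. Dated to the injections, it can put a microneedling effect on the wrong side of that line. A relatedness question that does not name microneedling leaves the investigator no defined answer for half of the sequence.

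What is at stake is the safety half of the objective. The precautions in the Bellafill instructions (Appendix 4) warn of a possible inflammatory reaction at the implant site when the filler is given before skin has fully healed from a procedure that relies on an active dermal response. Section 1.3 describes microneedling as wounding meant to stimulate healing, so it plausibly belongs to that class. An unresolved skin sign at Week 12 is then among the more informative observations the trial could make, and it is the kind of sign the literal rule can remove.

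**Working it through.** The plan gives no figure on this point to reproduce, and Section 12.1 offers no formal justification for the 45 subjects. The check sets the rules against the schedule, followed by a count of exposure.

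**Rules against the schedule**

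| Sign starting after Day 0 microneedling | Is it an AE? | Attribution |
|---|---|---|
| Resolves before Week 12, either track | Yes, under the opening definition; AEs are assessed at Visits 2, 3 and 4. Dropping it would need a strained, retroactive reading | No microneedling category |
| Track A, present at Week 12, later worsens or recurs after recovery | Yes, through the exception | No microneedling category; the injection is the only procedure named |
| Track A, present at Week 12, neither worsens nor recurs | No, on a literal reading: it predates the injections | Not reached |
| Track B, present at Week 12 | Rule has no Bellafill date to act on; the opening definition remains | No microneedling category |

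Two undefined terms decide how far this goes.

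- *Study injections.* Appendix 4 calls the skin test a test injection, and it is placed at Week -4. If it counts, the third row becomes an AE and Track B has a date. The attribution column does not change.
- *Study device.* Exclusion 9 in Section 4.4 describes it by Bellafill's components (lidocaine, with bovine collagen allergy alongside). Section 5.2, however, calls the roller a device. If the roller is included, one pooled answer still cannot tell microneedling from filler. The same term sets the start of AE follow-up in Section 11, and the unexpected-device-effect definition in Section 11.1.3 depends on an event being device-related.

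**Exposure**

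Inputs: 45 subjects (Section 12.1); 1:1 allocation (Section 7.4), so 22.5 per track; 1 month = 28 days (Section 10.1); first Bellafill at Week 12; Track B exit at Week 24. The Section 10.1 footnote places Track A exit 6 months (24 weeks) after the last injection:

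- no touch-up: 12 + 24 = Week 36
- touch-up at Month 1 (Week 16): 16 + 24 = Week 40

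Section 10.3.3 counts from Visit 4 instead, which gives Week 36 and stays within the range. Assumed: no dropout and nominal visit dates.

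Person-weeks before or without Bellafill treatment: 45 × 12 + 22.5 × 12 = 540 + 270 = 810.

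Total person-weeks after Day 0:

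- exit at Week 36: 22.5 × 36 + 22.5 × 24 = 810 + 540 = 1350; share 810/1350 = 60%
- exit at Week 40: 22.5 × 40 + 22.5 × 24 = 900 + 540 = 1440; share 810/1440 = 56%

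With whole subjects (22/23 either way) the range is 55.5% to 60.7%. By track, the share is 12/36 to 12/40 (33% to 30%) in Track A and 24/24 (100%) in Track B.

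**The case against.** The case for leaving the text alone is substantial. The opening definition covers the whole of participation and does not depend on relatedness. AEs are assessed at Screening, at all three microneedling visits and at every later visit. Onset dates allow events to be sorted around Visit 4, and a cause can be written for each. Section 12.3 tabulates all AEs and lists every report. Track B is a randomized concurrent comparator to Week 24. The exclusion speaks of disease signs and symptoms and has an exception. The key terms are ambiguous rather than plainly confined to the filler. The study is an open-label pilot with descriptive safety analysis.

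Most of this stands, and it rules out several stronger conclusions that a reader might draw:

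- That the AE definition as a whole is keyed to injections. Only the pre-existing-condition sentence is.
- That the safety tables would describe the filler only. Section 12.3 sets no such limit.
- That lingering microneedling effects could not be separated from filler effects. Recorded onset dates and the Track B comparison allow separation for events that are recorded.
- That Track B events are excluded. There the rule lacks a clear date; it does not remove events.
- That the roller certainly falls outside the study device. The usage points that way but is not settled.

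Two things survive. Sorting by date cannot recover a sign that the rule kept from counting as an AE. And a recorded cause has no defined categories and feeds no planned table, so it does not replace a relatedness item.

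**Conclusion.** The point holds in a limited form. Microneedling events are within the AE definition, but two stated rules do not fit a sequence that begins with microneedling.

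The attribution gap is the firmer of the two. It applies to Period I for all of the roughly 45 subjects and to the whole of Track B, and it remains under either reading of *study injections*. A reading of *study device* that includes the roller softens it without giving microneedling its own category.

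The exclusion problem is narrower. It needs the literal reading, in which *study injections* means Bellafill treatment, and it reaches only Track A subjects (about 22) who have a sign at Week 12 that neither worsens nor recurs. The documents give no rate for such signs, so the number lost cannot be estimated.

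The 56% to 60% describes exposure that the injection-based wording does not fit, given 45 subjects, equal allocation, no dropout and nominal dates. It does not measure under-reporting. No sample size, power or significance level changes. This should be fixed before enrolment, because attribution assigned in retrospect is less reliable, but it does not undermine the trial.

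**What to change.** - **Section 11.1.1:** date the pre-existing-condition rule to before the first study procedure, which is the Screening skin test. Dating it to Visit 1 would create a similar gap: a skin-test reaction that begins between Week -4 and Day 0 and persists would count as pre-existing, although Section 10.2.1 asks for AEs after skin testing.
- **Definitions:** define *study device* and *study injections*, and say which includes the roller and the skin test.
- **Section 11.1.5 and synopsis:** record relatedness separately to (a) the microneedling device or procedure, (b) Bellafill or its injection procedure, and (c) the skin test.
- **Section 12.3:** tabulate AEs from Day 0 to Visit 4 pooled, then Period II by track, and by relatedness category. Compare the tracks over the shared window to Week 24, cut by onset date, because a Track A subject with a touch-up has the 3-month visit at Week 16 + 12 = 28.
- **Section 11.1.2:** reconcile the filler-only yardstick for common responses with the microneedling period. Which responses count as usual is for the sponsor and investigators to settle.

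The cost is protocol wording, an extra relatedness item in the eCRF and a few table shells. No visit or procedure is added.

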11.1.2 Common Treatment Responses (CTRs)

Common Treatment Response (CTRs) following the use with a dermal filler include redness, pain, tenderness, firmness, swelling, lumps/bumps, bruising, itching and discoloration. CTRs will not be recorded as AEs unless the duration and/or severity are in excess of that typically observed following injection of a dermal filler, and are clinically significant as determined by the Treating Investigator.

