Among the 391 subjects treated with Bellafill, adverse events with reported onset dates 3 months or more after treatment were lumpiness at the injection site (6), rash and itching (3), sensitization reaction (2), increased sensitivity (2), persistent swelling and redness (1), granuloma or granulomatous inflammation (1), alopecia areata (1), visibility of the puncture site (1), and redness and visible capillaries near the area of injection (1).

Among the 123 Control subjects, adverse events with reported onset dates 3 months or more after treatment were abscess (1), infection (1), lumpiness (1), acneiform reaction (1), flu-like symptoms (1), persistent swelling or redness (1), and trauma fatality not related to the implant (1).

b) U.S. Controlled Acne Scar Clinical Trial

The U.S. Acne Scar pivotal study (Study SUN-11-001) involved 147 treated subjects at 10 centers. At baseline, subjects were randomized to receive Bellafill in the cheeks or saline (Control group). At 6 months, all Control subjects were eligible to receive treatment with Bellafill.

Of the 147 subjects treated in the study, 143 subjects received a treatment with Bellafill at either baseline/Day 0 (Period I) or at Month 6 (Period II, Track B). Therefore the safety information reflects the combination of patient outcomes for the initial (n=97) and crossover (n=46) Bellafill subjects (i.e., 97 + 46 = 143 total) compared to the 50 subjects who were initially enrolled in the Control treatment arm.

1. Subject Diary:

Subjects were asked to keep diary cards and grade symptoms of erythema, swelling, bruising, pain, itching, lumps/bumps and discoloration. Subjects' scores for the severity of these events after initial treatment are presented in **Table 2** and durations are provided in **Table 3**,respectively.

Subjects who observed any signs or symptoms (89.2%), experienced them shortly after Bellafill treatment and the majority were mild to moderate in intensity. Subjects typically reported these diary card symptoms as resolved in 1-7 days. Similar subject diary outcomes were notedfollowing touch-up treatment injections.

Table 2: Maximum Intensity of Signs/Symptoms After Initial Bellafill Treatment From Subject Diary (n=130)*

Sign/Symptom (R&L side combined)	None n (%)	Mild n (%)	Moderate n (%)	Severe n (%)
Any sign/symptom	14 (10.8%)	54 (41.5%)	51 (39.2%)	11 (8.5%)
Swelling	40 (30.8%)	48 (36.9%)	38 (29.2%)	4 (3.1%)
Erythema	44 (33.8%)	60 (46.2%)	23 (17.7%)	3 (2.3%)

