I	nfluenza	1 (0.7%)	1	0 (0.0)	0
Influen	za-like illness	2 (1.4%)	2	2 (4.0%)	3
M	Ieningitis	1 (0.7%)	1	0 (0.0)	0
Naso	opharyngitis	4 (2.8%)	4	0 (0.0)	0
Ora	al infection	0 (0.0)	0	1 (2.0%)	1

Suneva Medical, Inc. CONFIDENTIAL

		1	
	1		0
	1		1
2 (1.4%)	2	0 (0.0)	0
1 (0.7%)	1	0 (0.0)	0
5 (3.5%)	5	5 (10.0%)	5
2 (1.4%)	2	0 (0.0)	0
2 (1.4%)	2	2 (4.0%)	2
0 (0.0)	0	1 (2.0%)	1
1 (0.7%)	1	0 (0.0)	0
0 (0.0)	0	1 (2.0%)	1
0 (0.0)	0	1 (2.0%)	1
10 (6.9%)	15	2 (4.0%)	2
1 (0.7%)	1	0 (0.0)	0
1 (0.7%)	1	0 (0.0)	0
1 (0.7%)	1	0 (0.0)	0
2 (1.4%)	2	0 (0.0)	0
1 (0.7%)	1	0 (0.0)	0
1 (0.7%)	1	0 (0.0)	0
1 (0.7%)	1	1 (2.0%)	1
2 (1.4%)	4	0 (0.0)	0
1 (0.7%)	1	0 (0.0)	0
1 (0.7%)	1	0 (0.0)	0
1 (0.7%)	1	1 (2.0%)	1
	2 (1.4%) 2 (1.4%) 0 (0.0) 1 (0.7%) 0 (0.0) 10 (6.9%) 1 (0.7%) 1 (0.7%) 2 (1.4%) 1 (0.7%) 1 (0.7%) 2 (1.4%) 1 (0.7%) 1 (0.7%) 1 (0.7%) 1 (0.7%) 1 (0.7%) 1 (0.7%)	1 (0.7%) 1 2 (1.4%) 2 1 (0.7%) 1 5 (3.5%) 5 2 (1.4%) 2 2 (1.4%) 2 0 (0.0) 0 1 (0.7%) 1 0 (0.0) 0 0 (0.0) 0 10 (6.9%) 15 1 (0.7%) 1 1 (0.7%) 1 1 (0.7%) 1 1 (0.7%) 1 1 (0.7%) 1 1 (0.7%) 1 2 (1.4%) 4 1 (0.7%) 1 1 (0.7%) 1 1 (0.7%) 1 1 (0.7%) 1	1 (0.7%) 1 1 (2.0) 2 (1.4%) 2 0 (0.0) 1 (0.7%) 1 0 (0.0) 5 (3.5%) 5 5 (10.0%) 2 (1.4%) 2 0 (0.0) 2 (1.4%) 2 2 (4.0%) 0 (0.0) 0 1 (2.0%) 1 (0.7%) 1 0 (0.0) 0 (0.0) 0 1 (2.0%) 10 (6.9%) 15 2 (4.0%) 1 (0.7%) 1 0 (0.0) 1 (0.7%) 1 0 (0.0) 1 (0.7%) 1 0 (0.0) 1 (0.7%) 1 0 (0.0) 1 (0.7%) 1 0 (0.0) 1 (0.7%) 1 0 (0.0) 1 (0.7%) 1 0 (0.0) 1 (0.7%) 1 0 (0.0) 1 (0.7%) 1 0 (0.0) 1 (0.7%) 1 0 (0.0) 1 (0.7%) 1 0 (0.0) 1 (0.7%) 1 0 (0.0) 1 (0.7%) 1 0 (0.0)

^{*} n=143 is based on 97 subjects treated with Bellafill from Study Period I and 46 Period II Control subjects that crossed over and were treated with Bellafill

Five serious adverse events (SAEs) were noted during the study; cholecystitis, lower-back nerve impingement, recurrence of breast cancer, West Nile meningitis and exacerbation of depression. None were deemed related to study treatment. There were no deaths during the study.

Adverse events of special interest were followed separately for the study. These included hyper and hypopigmentation, hypertrophic scarring or keloid formation and the appearance of granulomas. None of these adverse events were reported.

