A total of 177 device-related AEs among 118 treated subjects were observed. Of the 177 treatment-related adverse events, the majority (131, 74%) were mild in severity. Forty-two (24%) of these related events were moderate in severity and four (2.0%) were considered severe. The most commonly reported device related adverse events were "lumpiness at the injection site" (29%) followed by "redness" (11%) see **Table 7**.

The duration of device related adverse events is provided in **Table 8**. Most of the device related adverse events were resolved during the study period. Thirty two related adverse events (18%) were deemed to be ongoing. The number of device related adverse events observed within the first month, 1-6 months, and beyond 6 months were comparable. The most common ongoing device related event was "lumpiness at the injection site" (12, 7%).

TABLE 7: Summary of Device-Related Adverse Event Severity (N=1008)

AE Category	Device-	Related AE	Severity	
AL Category	Mild	Moderate	Severe	Total
Lumpiness at injection site	46	6	0	52
Redness	19	1	0	20
Other local complications	13	5	0	18
Granuloma or enlargement of the implant	7	9	2	181
Swelling	8	8	1	17
Pain/ Tenderness	10	4	0	14
Skin blanching or discoloration at injection site	6	3	0	9
Increased sensitivity	8	0	0	8
Itching and/or burning	7	0	0	7
Other systemic complications	0	4	0	4
Hardness at the injection area	1	1	1	3
Rash	2	0	0	2
Scab and/or Scar	0	1	0	1
Recurrence of pre-existing Herpes labialis	1	0	0	1
Tingling, numbness, temp pain in various areas of the body	1	0	0	1
Stinging	1	0	0	1
Small veins in the implant area	1	0	0	1
Total	131	42	4	177

¹These 18 events occurred in 17 subjects. One subject had bilateral, biopsy-proven granuloma

Table 8: Summary of Device-Related Adverse Event by Duration

		Device-Related AE by Duration				
AE Category	≤ 30 days	31-180 days	>180 days	On Going	Missing ¹	Total
Other systemic complications	2	0	1	1	0	4
Other local complications	5	5	3	4	1	18
Lumpiness at injection site	8	11	19	12	2	52
Redness	7	6	6	1	0	20
Swelling	12	2	2	1	0	17
Granuloma or enlargement of the implant	0	3	5	10	0	18 ²
Pain/ Tenderness	6	2	6	0	0	14
Itching and/or burning	2	2	2	1	0	7
Increased sensitivity	1	2	5	0	0	8
Skin blanching or discoloration at injection	5	2	1	1	0	9
Rash	1	0	1	0	0	2
Hardness at the injection area	0	1	1	1	0	3
Scab and/or Scar	0	1	0	0	0	1
Recurrence of pre- existing Herpes labialis	1	0	0	0	0	1

Tingling, numbness, temp pain in various areas of the body	1	0	0	0	0	1

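### Section 11.1.2 lets a filler reaction that outlasts the usual course go unrecorded as an AE unless the unblinded treating investigator also calls it clinically significant, so persistent mild reactions in Track A can be under-counted

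*Combined protocol and SAP*

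**What the plan says.** Section 11.1.2 lists the common treatment responses (CTRs) of a dermal filler. They "include redness, pain, tenderness, firmness, swelling, lumps/bumps, bruising, itching and discoloration". The recording rule follows: "CTRs will not be recorded as AEs unless the duration and/or severity are in excess of that typically observed following injection of a dermal filler". A second condition is joined to this one: "and are clinically significant as determined by the Treating Investigator". The protocol gives no number of days, no grade and no criterion for either condition.

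Section 11.1.1 is wider: "An AE is defined as any undesirable physical, psychological or behavioral effect experienced by a subject during his/her participation in a study". It sets no significance condition. Among the commonly reported AEs of earlier studies it names "skin discoloration, increased sensitivity, telangiectasias in implant area, scar, edema, erythema", and further on itching, pain or tenderness, and granuloma formation. Section 11.1.4 provides a Mild grade for symptoms that are hardly noticed or cause no discomfort.

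Section 7.4 states that the study is open-label. Section 9 collects AEs by a general question, followed by directed questioning and examination as appropriate. The schedule in 10.1 has no subject diary and no CTR form. Section 12.3 tabulates AE incidence and severity and lists the reports.

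**The concern.** The two conditions in 11.1.2 are joined by *and*. A lump still palpable at Month 6 can meet the first and still stay off the AE form because the treating investigator does not consider it clinically significant. Symptoms that are barely noticed or not uncomfortable are the ones most easily judged that way, and they are also what the Mild grade exists to record.

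Safety is half of the study objective, and AEs are its only planned measure. Bellafill contains non-absorbable microspheres, so a persistent local sign is a result of interest even when it is mild. The appended acne scar study had two routes that this study lacks. Subjects graded local signs on diary cards, and certain events were followed separately: "These included hyper and hypopigmentation, hypertrophic scarring or keloid formation and the appearance of granulomas". If the AE form is the only route and the rule narrows it by opinion, a low or zero rate of local AEs in Track A cannot be read as absence of persistent reactions.

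**Working it through.** The plan gives no expected AE rate and no sample size calculation, so there is no design figure to reproduce. The check has two parts.

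**1. Reading the rule.**

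| Sign after Bellafill | Beyond typical duration or severity? | Called clinically significant? | AE under 11.1.2? | Undesirable effect under 11.1.1? |
|---|---|---|---|---|
| Lump, firmness or discoloration | no | any | no | yes, if undesirable |
| Same | yes | no | **no** | **yes, if undesirable** |
| Same | yes | yes | yes | yes |

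The middle row is the gap. Because a second condition can only remove events, the count under 11.1.2 is equal to or lower than the count under excess duration or severity alone; it is never higher. No other route recovers the removed events: 10.1 has no diary or CTR form and 12.3 has no CTR table. Apart from device malfunctions, an unexpected adverse device effect in 11.1.3 must first be a device-related AE.

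**2. Scale, from the acne scar study in Appendix 4.**

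Inputs:
- 143 Bellafill subjects; 14 had a treatment-related AE, 14 events in all (text and Table 6).
- Four were injection site reactions: three unresolved and one of 76 days (Table 6 and its footnote).
- One was an implant site mass of 180 days (Table 6).
- The only non-mild related events were one moderate injection site reaction and one severe bruise (text before Table 5).

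So 4 + 1 = 5 long-lasting lump-type events occurred in 5 subjects. One was moderate and 4 were mild. The rate is p = 5/143 = 3.5%.

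About 45 subjects allocated 1:1 (4.1, 7.4) give n = 22 or 23 in Track A if all reach Visit 4. Let *s* be the share of such events judged clinically significant. The documents give no value for *s*, so it is an assumption, shown over a range. Expected recorded subjects = n × p × s; chance of at least one recorded = 1 − (1 − p × s)^n.

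| s (assumed) | Expected, n = 22 | Chance of ≥1, n = 22 | Expected, n = 23 | Chance of ≥1, n = 23 |
|---|---|---|---|---|
| 1 (no second condition) | 22 × 5/143 = 0.77 | 54% | 0.80 | 56% |
| 0.5 | 0.38 | 32% | 0.40 | 33% |
| 0.2 (only the non-mild one of five) | 0.15 | 14% | 0.16 | 15% |

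The last row is an extreme: it supposes that every mild event fails the second condition, which the protocol does not say.

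**3. Visit timing for a recording rule.** With 1 month = 28 days (10.1), a touch-up at Visit 5a falls at the latest on day 28 + 7 = 35 after Visit 4. If Visit 6a is timed from Visit 4 (10.3.2), its earliest day is 84 − 7 = 77. The gap is 77 − 35 = 42 days, or 6 weeks. If it is timed from the last injection (footnote to 10.1), the gap is at least 77 days. Visit 7a is later in either case.

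**The case against.** The strongest reply is that the text shows a possibility and not a result. That stands. A reader might infer that filler harms *are* under-counted, or take the Appendix 4 figures as its size. The documents do not support either:

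- **Mild shares.** In the 5-year study, "Of the 177 treatment-related adverse events, the majority (131, 74%) were mild in severity", and 46 of 52 lumpiness events (88%) were mild. These are events that were recorded, in another study. Nothing equates mild with not clinically significant.
- **Injection site reactions in 6 of 143.** That is the all-cause count in Table 4. Related reactions were 4 of 143.
- **Granulomas.** A reader might infer that they are exempt because they present as lumps. Section 11.1.1 names granuloma formation as an AE, and it is not on the CTR list. Onset is also mostly too late: in Table 9, 1 of 17 began within 6 months of the last treatment.
- **A cut-off from the diary.** Appendix 4 says "Subjects typically reported these diary card symptoms as resolved in 1-7 days", and Table 3 ends with a band of 8–14 days. It is tempting to conclude that anything beyond 14 days is over-long. Table 3 has no later band, and the same study reports related events of 17–18, 76 and 180 days. It fixes no limit.
- **Bias between tracks.** Track B receives no filler, so it has no filler reactions to filter, and 12.3 plans tabulation, not a test between tracks.

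It can also be said that the AEs listed in 11.1.1 are a history of previous studies, that 12.3 promises a complete listing including unexpected events, and that photographs and global ratings at Visit 7a could show visible worsening. The first weakens the overlap in named signs but leaves the general definition in 11.1.1, which has no significance condition. The others do not close the gap: a listing shows only what was recorded, and photographs and ratings are not AE data.

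**Conclusion.** The concern holds in a limited form. As written, 11.1.2 allows a filler reaction of excess duration or severity to go unrecorded on the opinion of an unblinded investigator. This does not agree with 11.1.1 or with the purpose of the Mild grade, and nothing else in the plan captures the excluded signs. The direction is certain: an equal or lower AE count. The size is unknown, because it depends on the share judged clinically significant. If rates resemble the appended acne scar study, which did not use microneedling first, the events at issue amount to about 0.8 expected subjects in Track A. That is small in number, but with 22 subjects one event is 1/22 = 4.5%, so one unrecorded case can separate a reported rate of zero from a signal. The gap concerns the undiagnosed lump, firmness or pigment change. The change is worth making because it costs almost nothing and protects the only safety measure.

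**What to change.** In 11.1.2, delete "and are clinically significant as determined by the Treating Investigator" and keep clinical significance as a separate eCRF field. Add a sentence such as: *Any CTR sign that is new or worsened since before the first Bellafill injection and is present at Visit 6a or 7a is recorded as an AE with onset, duration and severity.*

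The words on new or worsened signs are needed because 11.1.1 excludes conditions that existed before the injections, and the ASAS in Appendix 1 allows macular discoloration even at its Clear grade. Visits 6a and 7a are at least 6 weeks after the last injection on either reading of the schedule. Extending the sentence to Visit 5a (day 21 to 35 after Visit 4) is the sponsor's choice, since the documents set no cut-off there.

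The cost is two edits to 11.1.2, one eCRF field and a few more AE records. AE assessment already takes place at these visits, so no visit or procedure is added. Reported AE incidence in Track A may look slightly less favourable.
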